## 1.2 Background and rationale for AZD9291

AZD9291 is a potent irreversible inhibitor of both the single mutant EGFRm (TKI sensitivity conferring mutation) and double mutant EGFRm/T790M (TKI resistance conferring mutation) receptor forms of EGFR with a significant selectivity margin over wild-type EGFR (Collett 1994, Cross et al 2014). AZD9291 can effectively block EGFR signalling both in EGFR single mutant cells with sensitising EGFR mutations and in double mutant cells bearing both the primary EGFR sensitising and secondary resistance T790M mutation (Collett 1994, Cross et al 2014). Preliminary data from an ongoing phase I study (D5160C00001) in EGFRm/T790M NSCLC patients has shown good evidence of anti-tumour activity while administration of AZD9291 has shown good tolerability across a range of doses (Ranson et al, Janne et al 2014).

In the clinical programme, at the data cut-off (DCO) of 1 August 2014, a total of 253 patients had received at least one dose of AZD9291 in study D5160C00001 (31 in the dose escalation cohorts and 222 in the dose expansion cohorts). A total of 138 patients had tumour harbouring the T790M mutation as assessed by central testing. The median age was 60 years and 62% of patients were female, 62% of patients were Asian and 36% were Caucasian, and 60% of patients had received immediate prior EGFR-TKI therapy. For all evaluable patients, confirmed Response Evaluation Criteria In Solid Tumours (RECIST 1.1) responses were observed at all dose levels (20–240 mg once daily). For the 78 patients with centrally tested T790M tumours and confirmed response, the longest duration of response is ongoing at >11 months. Preliminary median duration of response at 80 mg was 8.2 months. Preliminary median progression-free survival was 9.6 months (30% maturity, 41/138 events) (Yang et al 2014).

For further clinical details please refer to the AZD9291 Investigator's Brochure (IB).

## 1.3 Rationale for dose selection

The selected AZD9291 starting dose of 80 mg is the recommended phase II dose, as defined from study D5160C00001 (AZD9291 IB). This is not the maximum tolerated dose (MTD) as AZD9291 was administered up to 240 mg daily with no dose-limiting toxicity (DLT) observed. In the phase III registration study, the same dose of 80 mg AZD9291 is used.

## 1.4 Benefit/risk and ethical assessment

### 1.4.1 Nonclinical data

In a modified embryofetal development study in the rat, AZD9291 caused embryoletality when administered to pregnant rats prior to embryonic implantation, at a maternally tolerated dose of 20 mg/kg (approximately 1.4x the recommended human dose of 80 mg daily). It is not known whether AZD9291 is excreted in human milk. Women of childbearing potential and men must use adequate contraception prior to study entry, for the entire duration of study participation. Women who are breast feeding are excluded from the study. Both women and men must be fully informed of the reproductive toxicity testing, and women must have a negative pregnancy test prior to enrolment (refer to inclusion criteria 8 and 9).

For further preclinical detail please refer to the AZD9291 IB.

### 1.4.2 Clinical data

At the time of this protocol writing, one phase I study (study D5160C00005) was completed and 15 studies are ongoing. A total of 945 subjects were exposed to AZD9291, including 93 subjects exposed to a combination of AZD9291 plus another treatment and 45 healthy volunteers exposed to a single dose of AZD9291 20 mg. Dose levels of AZD9291 ranged from 20 to 240 mg, with exposure ranging from 1 to 609 days. The emerging safety profile is based on preliminary data from studies with AZD9291 using a DCO of 16 January 2015.

The key efficacy findings from the clinical programme at the DCO of 01 Aug 2014 are summarised below:

- Treatment with AZD9291 has resulted in tumour shrinkage (including an effect on brain metastases) with objective response rates (ORRs) for the dose cohorts in the D5160C00001 study ranging from 43% to 58% for the population of  $\geq 2^{\text{nd}}$  line patients as a whole.
- Patients with tumors harboring the T790M appeared to have improved responses (ORRs in these patients ranged from 50% to 70%) compared with responses in patients with tumors without the presence of T790M.
- Responses were durable, with the preliminary median duration of response calculated as 8.2 months for the 80 mg dose in patients with tumors harboring the T790M. Preliminary median PFS was 9.6 months in patients with centrally tested T790M+ NSCLC (30% maturity, 41/138 events) and 2.8 months in patients with centrally confirmed T790M negative NSCLC (71% maturity, 44/62 events).
- The most commonly reported adverse events (AEs) were rash, diarrhoea, pruritus and nausea. The most common SAEs by System Organ Class (SOC) were respiratory, thoracic and mediastinal disorders, gastrointestinal disorders, metabolism and nutrition disorders, and blood and lymphatic system disorders (Table 1).
- A total of 23 deaths were reported across all studies with AZD9291, for which the cause of death was not attributed by the Investigator to their underlying disease. Of

these, 1 death was considered by the Investigator to be related to AZD9291 treatment (an event of respiratory failure/left lung interstitial lung disease (ILD) reported in the D5160C00002 study). A further 62 patients died while participating in studies with AZD9291, but for whom the cause of death was attributed to their underlying disease; of these deaths, 2 were considered by the Investigator to be related to AZD9291 treatment by the Investigator (an event of sepsis/pneumonia/lung cancer and an event of ILD, both reported in the D5160C00001 study).

Table 1 shows the most common SAEs observed at safety DCO in the ongoing clinical studies considered to be related to AZD9291 treatment by the Investigators, by Medical Dictionary for Regulatory Activities (MedDRA) SOC and Preferred Term (PT).

**Table 1 Most common ( $\geq 2$ ) SAEs observed to date in the ongoing AZD9291 clinical studies considered related to AZD9291 treatment**

MedDRA SOC and PT	Number of events
Respiratory, thoracic and mediastinal disorders	15
Pneumonitis	8
Interstitial lung disease	4
Pulmonary embolism	2
Gastrointestinal disorders	9
Diarrhoea	5
Nausea	2
Metabolism and nutrition disorders	6
Decreased appetite	3
Dehydration	2
Blood and lymphatic system disorders	3
Thrombocytopenia	2
Infections and infestations	3
Investigations	3
Nervous system disorders	2
General disorders and administration site conditions	2
Skin and subcutaneous tissue disorders	2

**Abbreviations:** MedDRA Medical Dictionary of Regulatory Activities; PT preferred term; SOC system organ class.

#### 1.4.2.1 Study D5160C00005

A total of 32 healthy male volunteers were enrolled in this study: 16 subjects in Part A (the relative bioavailability part of the study) and 16 subjects in Part B (the food effect part of the study). All healthy volunteers received a single dose of 20 mg AZD9291, either as an oral solution, tablet, or capsule formulation. Part B of the study was conducted using the tablet formulation only. There were no deaths or SAEs reported during the study. There were no events leading to discontinuation during Part A of the study. One healthy volunteer had an

event of alanine aminotransferase increased of mild intensity which led to discontinuation during Part B of the study; this event was considered to be related to AZD9291.

In Part A, 10 out of the 16 healthy volunteers (62.5%) reported at least one AE. The most commonly reported AEs were in the SOC “infections and infestations” (5 AEs); within this SOC, the most commonly reported PT, was influenza (3 out of 16 healthy volunteers [18.8%]). All other PTs were reported in 1 healthy volunteer only. A similar pattern of AEs was observed in Part B, where 6 out of 16 volunteers (37.5%) reported at least one AE. In Part B, the most commonly reported AEs were also in the SOC “infections and infestations” with 2 AEs (PT upper respiratory tract infections). All other PTs were reported in 1 healthy volunteer only.

#### **1.4.2.2 Study D5160C00001**

##### ***Phase I (dose escalation and expansion)***

The following data are based upon the phase I database lock performed on December 2014. No new or relevant safety data have been reported in patients receiving AZD9291 in this phase I study subsequent to this time point. Exposure ranged from 2 to 609 days. The MTD of AZD9291 in patients with advanced NSCLC was not established as the DLT criteria were not met at doses as high as 240 mg. Although a DLT was not identified as defined in the protocol, dose interruptions, dose reductions and EGFR wild type effects were observed at higher frequencies at the 160 mg and 240 mg dose levels. Adverse events were reported in 97% of patients, SAEs were reported in 24% (87/362) of patients. The majority of AEs were mild to moderate in intensity (Common Terminology Criteria for Adverse Event [CTCAE] Grade 1 or 2), and 37.8% (137/362) of patients reported CTCAE Grade  $\geq 3$  events. In the overall study population, a total of 11 fatal AEs were reported, only one of which (pneumonia) was considered by the Investigator to be related to AZD9291.

##### ***Phase II (extension phase)***

In the Phase II study, at the safety DCO, 201 patients had received treatment with 80 mg AZD9291. A pre-planned preliminary database lock was performed on November 2014 and safety data are based upon this database lock. No new or relevant safety data has been reported in patients receiving AZD9291 in this phase II study subsequent to this time point. Exposure ranged from 0.1 to > 6.0 months, with 55.5% (111/201) of patients receiving treatment for a total duration of 3 to 6 months. Adverse events were reported in 87% (174/201) of patients, severe AEs (CTCAE Grade  $\geq 3$ ) were reported for 13.5% (27/201) of patients. The majority of AEs were mild to moderate in intensity (CTCAE Grade 1 or 2). The most commonly reported AEs (in >5% of patients) were diarrhoea, rash, and paronychia. These AEs are consistent with the most frequently reported AEs in the Phase 1 study. Serious AEs were reported in 10.5% (21/201) of patients on study treatment. A total of 4 patients had fatal AEs, 1 fatal AE of interstitial lung disease considered by the Investigator to be related to AZD9291 and 3 others fatal AEs were attributed to disease progression. The reported AEs infrequently led to AZD9291 dose modification or permanent discontinuation, with 1.5 % (3/201) of reported AEs resulting in permanent discontinuation of AZD9291.

#### **1.4.2.3 Study D5160C00002**

In study D5160C00002, at the DCO of January 2015, 210 patients had been exposed to 80 mg AZD9291 daily. Safety data are based on a pre-planned database lock (December 2014), and no new or relevant safety data have been identified from the study D5160C00002 subsequent to this time point. Exposure ranged from 0 to 5.7 months with the majority of patients receiving AZD9291 for a total duration of 3 to 6 months. Adverse events were reported in approximately 79% (166/210) of patients and were infrequently severe (12.9%, [26/210] of AEs were CTCAE  $\geq$  Grade 3). The majority of AEs were mild to moderate in intensity (CTCAE Grade 1 or 2). The most commonly reported AEs (in  $\geq$ 5% of patients) were diarrhoea, rash and dry skin. The types of AEs were consistent with the known safety profile of AZD9291. Serious AEs were reported in 9.4% (19/210) of patients on study treatment. One fatal AE occurred (dyspnoea) which was not considered to be related to AZD9291 or attributed to disease progression by the Investigator. The reported AEs infrequently led to AZD9291 dose modification or permanent discontinuation, with permanent discontinuation of AZD9291 due to AEs reported in <2% of patients.

#### **1.4.2.4 Study D5160C00003**

At the DCO of January 2015, 23 patients with advanced NSCLC had been exposed to AZD9291 in the study D5160C00003. A single case of pneumonitis was reported in one patient enrolled in the study D5160C00002 prior to dosing with AZD9291.

For further clinical detail please refer to the AZD9291 IB.

### **1.4.3 Conclusions**

Based on the identified and potential risks associated with AZD9291 treatment, this clinical study protocol incorporates safety monitoring procedures and guidance to assist with early diagnosis and rapid management of potential AZD9291 drug-related symptoms. Dose modification algorithms are also included in this clinical study protocol.

All trials of AZD9291 exclude patients with clinically significant toxicities related to prior treatments in addition to specifically excluding patients with a history of any of the following:

- Clinically active interstitial lung disease
- Current or concurrent risk factors for severe arrhythmias

Given the clinical activity noted to date with AZD9291, the acceptable safety profile demonstrated thus far, and the inclusion/exclusion criteria stipulated in this study protocol, it is reasonable and appropriate to make AZD9291 available to patients with NSCLC no longer responding to previous EGFR-TKI and whose tumors harbor the T790M mutation.

Cumulative summary tabulations of exposure by age/sex and by racial group are presented in [Table 2](#) and [Table 3](#), respectively.

**Table 2** Estimated cumulative subject exposure to AZD9291 from completed and ongoing clinical trials by age and sex

Age range (years)	Number of subjects		
	Male	Female	Total
<18	0	0	0
18-65	415	212	627
66-75	143	69	212
76-85	42	31	73
86-95	5	2	7
>95	0	1	1
Total	605	315	920

Data from completed and ongoing clinical trials as of 16 January 2015.

**Table 3** Estimated cumulative subject exposure to AZD9291 from completed and ongoing clinical trials by racial group

Racial group	Number of subjects
Asian	515
White	359
Black or African American	48
Other	13
American Indian or Alaska Native	4
Native Hawaiian or other Pacific Islander	2
Unknown	2
Total	945

Data from completed and ongoing clinical trials as of 16 January 2015.

The difference of 25 subjects between [Table 2](#) and [Table 3](#) is due to subjects with missing age and/or race data. These 25 subjects had dosing information and thus were considered to have received AZD9291 while enrolled in the study. However, due to missing age and/or race information these patients are counted in a different table (i.e., [Table 3](#)).

## **2. STUDY OBJECTIVE**

The primary objective of this study is to assess the efficacy and safety of single agent AZD9291 in a real world setting in adult patients with advanced or metastatic, epidermal growth factor receptor (EGFR) T790M mutation-positive Non-Small Cell Lung Cancer (NSCLC), who have received prior EGFR-tyrosine kinase inhibitor (TKI) therapy.

The primary efficacy outcome is OS, with secondary efficacy outcomes including investigator assessed response rate, investigator assessed PFS and Time to Treatment Discontinuation (TTD).

## **3. PATIENT SELECTION**

Each patient must meet all of the applicable inclusion criteria and none of the exclusion criteria for this Real World Treatment Study. Under no circumstances can there be exceptions to this rule.

### **3.1 Inclusion criteria**

For inclusion in the study patients must fulfill the following criteria:

1. Provision of signed and dated written informed consent by the patient or legally acceptable representative prior to any study-specific procedures
2. Adults (according to each country regulations for age of majority)
3. Locally advanced (stage IIIB) or metastatic (stage IV) EGFRm NSCLC, not amenable to curative surgery or radiotherapy, with confirmation of the presence of the T790M mutation
4. Prior therapy with an EGFR-TKI. Patients may have also received additional lines of treatment
5. World Health Organization (WHO) performance status 0-2
6. Adequate bone marrow reserve and organ function as demonstrated by complete blood count, biochemistry in blood and urine at baseline
7. ECG recording at baseline showing absence of any cardiac abnormality as per exclusion criterion #6
8. Female patients of childbearing potential must be using adequate contraceptive measures (see Restrictions, Section 4.2), must not be breast feeding, and must have a negative pregnancy test prior to start of dosing. Otherwise, they must have evidence of non-childbearing potential as defined below:
  - a. Post-menopausal defined as aged more than 50 years and amenorrheic for at least 12 months following cessation of all exogenous hormonal treatments
  - b. Women under 50 years would be consider post-menopausal if they have been amenorrheic for 12 months or more following cessation of exogenous hormonal

- treatments and with luteinizing hormone and follicle-stimulating hormone levels in the post-menopausal range for the institution
- c. Documentation of irreversible surgical sterilisation by hysterectomy, bilateral oophorectomy or bilateral salpingectomy but not tubal ligation
9. Male patients must be willing to use barrier contraception, i.e., condoms (see Restrictions, Section 4.2)

### 3.2 Exclusion criteria

Patients will not be enrolled in this study if any of the following exclusion criteria are met:

1. Previous (within 6 months) or current treatment with AZD9291
2. Patients currently receiving (or unable to stop use at least 1 week prior to receiving the first dose of AZD9291) any treatment known to be potent inhibitors or inducers of cytochrome P450 (CYP) 3A4 (Appendix B)
3. Any evidence of severe or uncontrolled systemic diseases, including uncontrolled hypertension, active bleeding diatheses, active infection\* including hepatitis B, hepatitis C and human immunodeficiency virus, or significantly impaired bone marrow reserve or organ function, including hepatic and renal impairment, which in the investigator's opinion would significantly alter the risk/benefit balance.

\* active infection will include any patients receiving intravenous treatment for any infection and patients with hepatitis B or C surface antigen (+) – Patients receiving oral antiviral suppressive therapy for hepatitis B or C will be permitted to enrol in the study.

4. Patient with symptomatic central nervous system (CNS) metastases who is neurologically unstable or has required increasing doses of steroids to manage CNS symptoms within the 2 weeks prior to start AZD9291 administration
5. Past medical history of ILD, drug-induced ILD, radiation pneumonitis requiring steroid treatment, or any evidence of clinically active ILD
6. Any of the following cardiac criteria:

- a. Mean resting corrected QT interval (QTcF) > 470 ms using Fredericia's formula :

$$QT_{cF} = \frac{QT}{\sqrt[3]{RR}}$$

- b. Any clinically important abnormalities in rhythm, conduction or morphology of resting ECG (e.g., complete left bundle branch block, third degree heart block, second degree heart block)
- c. Any factors that increase the risk of QTc prolongation or risk of arrhythmic events

7. Any unresolved toxicity from prior therapy CTCAE  $\geq$  grade 3 at the time of starting treatment
8. History of hypersensitivity to excipients of AZD9291 or to drugs with a similar chemical structure or class to AZD9291

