### **4.1 Study Plan**

This study has been subject to an internal review according to AstraZeneca standard procedures.

Concomitant treatments, other than anti-cancer treatments, should be taken according to local medical practice. There are no restrictions on concomitant use in this study except per exclusion criteria. However, it is advised that those medical products and other products known to have interactions with AZD9291 should be avoided (see [Appendix B](#)).

The latest version of the IB and any subsequent updates will be supplied to the investigator. Investigators need to become familiar with the content of the IB and appendices associated with this protocol.

[Table 4](#) below outlines data collection measures that are considered for this study:

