period (30 days post-last dose). Patients taking concomitant medications whose disposition is dependent upon CYP3A4 and breast cancer resistance protein and which have a narrow therapeutic index should be closely monitored for signs of changed tolerability as a result of increased exposure of the concomitant medication whilst receiving AZD9291. Patients taking concomitant medications whose disposition is dependent upon CYP3A4, CYP1A2, CYP2C or p-glycoprotein and which have a narrow therapeutic index should be closely monitored for reduction in therapeutic activity as a result of the reduced exposure of the concomitant medication while receiving AZD9291. Guidance on medications to avoid, medications that require close monitoring and on washout periods is provided (see [Appendix B](#)).

Up to 3-fold increase in exposure may occur in statin exposure when co-administered with AZD9291. It is recommended that the starting and maintenance dose of statins should be as low as possible and should be guided by the statin prescribing information.

Patients taking warfarin should be monitored regularly for changes in prothrombin time or international normalized ratio.

Patients who wear contact lenses must discontinue wearing their lenses if they have any mild to moderate eye symptoms (CTCAE grade  $\leq 2$ ) while receiving treatment with AZD9291 until at least one week after symptoms have resolved. If a patient has a recurrence of eye symptoms or experiences any severe (CTCAE grade  $\geq 3$ ) ocular events, they must discontinue wearing their contact lenses until at least one week after treatment with AZD9291 is permanently discontinued. Patients must not use any eye drops or ointment for treatment of eye symptoms, unless agreed to by a study doctor, at any time during the study until 1 week after AZD9291 has been permanently discontinued. Patients must consult their investigator promptly if they have any concerns.

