### Drugs inducing cyp3a4 metabolism that AstraZeneca strongly recommend are not combined with azd9291

AZD9291 is metabolised by CYP3A4 and CYP3A5 enzymes.

A drug-drug interaction study of AZD9291 evaluated in patients showed that there is potential for AZD9291 being a victim when co-administered with strong inducers of CYP3A4 (AZD9291 concentrations are decreased when co-dosed with rifampicin).

The following potent inducers of CYP3A4 must not be used during this study for any patient receiving AZD9291.

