**Table 6 Drugs inducing CYP3A4**

Contraindicated drugs	Withdrawal period prior to AZD9291 start
Carbamazepine, phenobarbital, phenytoin, rifampicin, rifabutin, rifapentin St John’s Wort	3 weeks
Phenobarbitone	5 weeks

This list is not intended to be exhaustive, and a similar restriction will apply to other agents that are known to strongly modulate CYP3A4 activity. Appropriate medical judgment is required. Please contact AstraZeneca with any queries you have on this issue.

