### 2.2 Violations and deviations

All major deviations related to the study inclusion or exclusion criteria and study conduct will be listed and summarised.

The following general categories will be considered major deviations. This list is not exhaustive and additional important deviations may be added prior to database lock.

- Informed consent procedure deviation Missing subject' signature from the informed consent document or other International Conference on Harmonisation - Good Clinical Practice (ICH-GCP) violation related to informed consent; laboratory or urinalysis samples or electrocardiogram (ECG) date before informed consent date and not performed per standard of care but on study purpose)
- Eligibility criteria deviation (any inclusion criteria not met or exclusion criteria met)
- Prohibited medication deviation (e.g., patients received other anticancer agents, investigational agents, or radiotherapy while on study treatment)
- Procedures/Tests deviation (ECG or ophthalmologic assessment or WHO performance status not performed at screening visit)
- Investigational product administration deviation (Overdose; Screening assessment date not within 28 days before start of treatment; Incorrect procedure for T790M obtainment; New or worsening pulmonary symptoms or radiological abnormality suggestive of Interstitial Lung Disease (ILD) observed, but study treatment not interrupted; Patient experiencing grade 3 QT interval corrected per Fredericia's formula (QTcF) with QTcF prolongation, but study treatment not interrupted)
- Withdrawal criteria deviation (Any withdrawal criteria met)
- Adverse Event (AE) / Serious Adverse Event (SAE) deviation (SAE / AE of special interest not reported in CRF within 24 hours of become aware)

The categorization of these as major deviations is not automatic and will depend on the duration and the perceived effect on efficacy.

All protocol deviations are defined in Protocol Deviation Specification document version 5.0 where a category Programmable / Observable is assigned to each deviation. Programmable deviations are programmed while Observable are checked manually during monitoring visits. Programmable deviations are then imported, and observable deviations are entered in a Protocol Deviation Tool according to classification defined in the Protocol Deviation

Specification. All deviations are then reviewed and classified on a monthly basis as Major/Minor.

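### Exclusion 2 accepts a 1-week stop for potent CYP3A4 inducers, Table 6 in the appendix it cites sets 3 or 5 weeks, and no text says which governs

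*Protocol*

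**What the plan says.** Protocol section 3 makes the eligibility criteria binding and allows no exceptions. Exclusion 2 in section 3.2 covers potent inhibitors and inducers of CYP3A4. It excludes a patient who is taking one now or is "unable to stop use at least 1 week prior to receiving the first dose of AZD9291", and it cites Appendix B.

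Appendix B prohibits the listed potent inducers for anyone receiving AZD9291. Table 6 calls them contraindicated and gives each a withdrawal period counted back from AZD9291 start. The row "Carbamazepine, phenobarbital, phenytoin, rifampicin, rifabutin, rifapentin", which also includes St John's Wort, carries 3 weeks. A separate row for phenobarbitone carries 5 weeks. The table is not a closed list: "a similar restriction will apply to other agents that are known to strongly modulate CYP3A4 activity".

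Section 4.2 (Restrictions), item 3, also sends the reader to Appendix B: "Guidance on medications to avoid, medications that require close monitoring and on washout periods is provided".

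**The concern.** The criterion that decides who may start treatment gives one minimum stop, and the appendix it cites gives a longer one for every inducer it names. A site that applies exclusion 2 literally can start a patient whom Table 6 would still hold back. A site that applies Table 6 will make the same patient wait. Both can say that they followed the protocol.

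What is at stake is exposure to the study drug early in treatment. Appendix B gives the reason for the restriction: "AZD9291 concentrations are decreased when co-dosed with rifampicin". That observation concerns taking the two drugs together. The withdrawal periods imply that the sponsor wants a margin after stopping as well, and exclusion 2 does not enforce that margin.

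**Working it through.** The plan has no statistical figure to reproduce here. The check sets the two rules side by side and counts days.

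**Inputs**
- Exclusion 2 (Protocol 3.2): minimum stop of 1 week = 7 days before first dose.
- Table 6, first row (Protocol Appendix B): 3 weeks = 21 days before AZD9291 start.
- Table 6, phenobarbitone row: 5 weeks = 35 days before AZD9291 start.
- Screening window (Protocol Table 4): 28 days before day 1.

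**Same anchor.** Both rules count back from the start of AZD9291, so the periods can be compared directly.

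**Days on which the rules disagree.** Let d be the number of days from the last inducer dose to the first AZD9291 dose. Exclusion 2 is passed when d ≥ 7. The Table 6 period is still running when d < 21, or d < 35 for phenobarbitone.
- 3-week drugs: d = 7 to 20, which is 20 − 7 + 1 = 14 days.
- Phenobarbitone: d = 7 to 34, which is 34 − 7 + 1 = 28 days.

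**Ratio of the minimum stops.** 21 / 7 = 3 and 35 / 7 = 5. For no drug in Table 6 is 1 week long enough.

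**Longest added wait if Table 6 governs.** 21 − 7 = 14 days, and 35 − 7 = 28 days.

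**Fit with screening, if the inducer is stopped at a visit on day −28.** The 3-week period ends with 28 − 21 = 7 days to spare. The 5-week period ends 35 − 28 = 7 days too late for that window.

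**The two similar rows.** Phenobarbital is in the 3-week row and phenobarbitone has its own 5-week row. In ordinary nomenclature these are two names for one drug. The documents do not say so, and I take it as an assumption. If it is right, a patient 21 to 34 days off that drug (34 − 21 + 1 = 14 days) satisfies one row and not the other.

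**The case against.** The strongest reply is that these are two tiers and not a contradiction. Exclusion 2 states a minimum, cites Appendix B in the same sentence, and is not breached by waiting longer. Section 4.2 points to Appendix B for washout, and section 4.1 expects investigators to know the appendices. A general floor with drug-specific periods on top is a natural reading. What stands is that a careful site can satisfy both texts. What does not follow is that every site must, because no sentence makes the longer period govern.

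A second reply is that Appendix B only advises. Its heading speaks of a strong recommendation, and section 4.2 calls it guidance. But the text under that heading is a prohibition, and Table 6 labels the drugs contraindicated. If it were advice only, the enforceable rule would be the 1-week stop, and the protocol would be advising at least three times the stop that it requires.

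A third reply is that no harm is shown, and that is correct. The rifampicin observation concerns co-dosing, the documents give no data on induction after stopping, and the study is single-arm and descriptive.

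The point about the phenobarbital and phenobarbitone rows also stands. Writing Table 6 into a no-exceptions criterion without reconciling them would leave eligibility for that drug undecided between 3 and 5 weeks. The fix has to deal with it.

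**Conclusion.** The conflict is in the current text and the criterion is wrong as written. Severity is minor. The gap is 14 days (d = 7 to 20) for the 3-week drugs and 28 days (d = 7 to 34) for phenobarbitone. The phenobarbitone figure takes its 5-week row at face value. The number of patients who fall in these gaps is not given, and no effect on OS, PFS, response rate or the precision of the OS estimate is claimed.

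Three stronger readings are tempting and are not supported.
- A reader might infer from section 4.1 ("There are no restrictions on concomitant use in this study except per exclusion criteria") that the shorter rule is meant to win. That sentence concerns drugs taken alongside AZD9291, not withdrawal before the first dose, so it does not settle precedence.
- A reader might infer that these patients would go unrecorded, because the SAP category in section 2.2 is "Eligibility criteria deviation (any inclusion criteria not met or exclusion criteria met". The SAP says its list is not exhaustive and refers definitions to a Protocol Deviation Specification that is not among the documents. Whether such a case would be flagged cannot be known.
- A reader might infer a parallel fault for inhibitors, since exclusion 2 bars them and Appendix B has no table of CYP3A4 inhibitors. The version history says that the inhibitor restriction in section 4.2 was removed because a study showed no effect of inhibitors on AZD9291. The sponsor could be asked whether exclusion 2 still intends to bar them, but no error is shown.

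**What to change.** In exclusion 2, keep the 1-week stop for potent inhibitors. For potent inducers, replace it with *at least the withdrawal period in Appendix B Table 6*. Inducers not named in the table stay under the existing sentence below it, which extends a similar restriction to them. In the same edit, reconcile the phenobarbital and phenobarbitone rows. Until that is done, apply 5 weeks to both names.

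The change is one criterion and one table, with no change to the analysis. A patient still on an inducer may start up to 2 weeks later than exclusion 2 now allows, or up to 4 weeks later under the 5-week row. In progressing disease that is a real cost to the patient.

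A 5-week stop begun at screening overruns the 28-day window by 7 days if screening is on day −28. SAP section 2.2 lists "Screening assessment date not within 28 days before start of treatment" among its deviations, so some assessments would have to be repeated. The extended screening visit in Protocol section 4.1 could hold them, but its text names only a serious adverse event as the reason for delay. Adding inducer withdrawal as a second reason would close that gap.
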